metabolism in 97.5% of the population.²⁰ While debate surrounds a sufficient range for 25(OH)D, there does seem to be a general acceptance that the optimum range is between 30 – 60 ng/mL.⁵⁻⁷ The human body uses sunlight as the primary source of vitamin D and produces large quantities efficiently with limited UVB exposure.¹²⁻¹⁵ Therefore, a rational way to determine the optimum vitamin D range is by studying natural cutaneous vitamin D synthesis. It has been demonstrated that a single session of full body exposure to solar radiation can produce a time-released equivalent of approximately 10,000 IU of oral vitamin D.¹⁶ A safe upper limit for vitamin D is related to oral intake only. Cutaneous vitamin D production is automatically regulated by a photochemical reaction and pigmentation, preventing toxicity.¹⁷⁻¹⁹ Consequently, hypervitaminosis D is not possible when the only vitamin D source is skin production following exposure to UVB light. For all these reasons, an innovative alternative to address low vitamin D status in adults, Warfighters included, is needed.

5 Study Objectives

The specific aims for this project were:

1. Determine acceptability and feasibility of a standing phototherapy kiosk designed as a self-care intervention for AD and retired service members, beneficiaries, and DA civilians;
2. Demonstrate that narrow spectrum UVB delivered by the SPK is at least equivalent to D3 oral intake to raise or maintain serum 25(OH)D levels over a 10-week intervention period;
3. Examine the relationship of demographic variables, including gender, age, body mass index, body fat, ethnicity, and sun exposure to serum 25(OH)D levels in both groups.

6 Investigational Plan

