All eligible adult volunteers will be enrolled regardless of their baseline 25(OH)D level as it is important in this non-inferiority study to show there is no potential for harm from phototherapy, even if the baseline 25(OH)D level is above 30 ng/mL. If the goal is to develop a self-care kiosk, individuals will not have the ability to check their serum vitamin D status prior to use. We also want to learn the trajectory of vitamin D absorption and availability over a 3-4-month period in order to make evidence-based therapeutic recommendations. It is not possible to blind the subjects or research team to the group assignment given the two comparators.

Serum levels of 25(OH)D, calcium, and parathyroid hormone are drawn at baseline (T0), immediately following the intervention at 10 weeks (T6); at 14 weeks (T8), 25(OH)D is drawn to document sustainment of treatment effect. Remuneration in the form of \$20 Amazon gift cards is provided to all volunteers after the baseline and final scheduled blood draw (as allowed by DoD Instruction 3216.02 Dated November 8, 2011).

A survey shall be completed at T1 and reviewed with participants again at the 10-week visit to capture relevant demographic, medical history, sun exposure, travel, daily activities, and dietary data. Active duty SMs shall report the number of days on profile (activity restriction) for the previous three months, at T1 and T6. A Device Usability Scale will be administered to the kiosk group participants upon protocol completion to address acceptability and feasibility of the treatment. With the assistance of a biostatistician, we will analyze data using repeated measures analysis of variance adjusting for significant covariates such as 25(OH)D level at baseline. Logistic regression analyses are used to predict outcomes and explain the interrelationships among variables, i.e. age, gender, BMI, body fat, ethnicity, and sun exposure relationship to 25(OH)D serum levels.

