6.5 Efficacy and Safety Variables

6.5.1 Efficacy and Safety Measurements Assessed

To determine that phototherapy is at least equivalent to D3 oral intake to raise or maintain serum 25(OH)D levels over a 10-week intervention period baseline 25(OH)D levels are obtained.

Blood draws will occur upon enrollment with two follow-up measurements, one at 10 weeks and a final level 4 weeks after completing the protocol to evaluate sustainment of the post-treatment level. Serum concentration of 25(OH)D is the best indicator of vitamin D status as it represents cutaneous production and consumption of food and supplements. Serum 25(OH)D has a circulating half-life of 15 days.²⁸ Serum 25(OH)D levels do not indicate the amount of vitamin D stored in body tissues.¹⁰ All blood levels will be obtained by experienced phlebotomists in the hospital central laboratory. There will be no standardization of time of day for the blood draw. An Endocrine consultant will review all abnormal lab values [(25OH)D, PTH, Calcium] and recommended follow-up with the Primary Care Manager, if necessary.

To determine acceptability and feasibility of the standing phototherapy kiosk, a Device Usability Scale will be administered to the Kiosk Group upon completion of the study. This 12-item Likert-type scale was adapted from the Digital Equipment Corporation "System Usability Scale" (1986). Questions assessed cleanliness, ease of use, and comfort of the kiosk with a Likert-type scale where 1= Strongly disagree to 5 = Strongly agree.

The research team will meticulously track the number of potential participants screened, the number of enrolled subjects, completion of all study timepoints, and attrition from each arm.

To examine the relationship of demographic variables, including gender, age, body mass index, body fat, ethnicity, and sun exposure to serum 25(OH)D levels in both groups, several other measurements will be obtained including the following:

1. Body height (Ht) – Vertical height is measured at baseline using a Harpenden Stadiometer and recorded to the nearest 0.1 cm. The stadiometer is composed of a rigid vertical backboard with an attached rigid horizontal headboard which moves up and down the backboard. Final height was the average of two measurements taken by trained study staff.

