6.5.3 Primary Efficacy Variable(s)

Serum 25(OH)D level is the primary endpoint used to establish whether the treatment in the phototherapy kiosk group is equivalent to the oral vitamin D3 supplementation currently prescribed as the standard of care. It is expected that the serum 25(OH)D levels in both groups will rise over time and that the serum 25(OH)D levels will be equal to, or not less than, that of the oral supplementation group.

A Device Usability Scale will be administered to the Kiosk Group to assess acceptability and feasibility. This 12-item Likert-type scale was adapted from the Digital Equipment Corporation

“System Usability Scale” (1986) and it will be administered to the Kiosk Group upon completion of the study.

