6.6 Statistical Methods Planned in the Protocol and Determination of Sample Size

6.6.1 Statistical and Analytical Plans

The original analysis plan will be carried out using all available subject data points. No interim analysis will be performed. Exploratory data analyses will be conducted on the serum vitamin D levels of participants assigned to either the oral vitamin D supplementation or kiosk group. The analysis will be restricted to participants with valid baseline serum vitamin D data and at least one follow-up blood draw. The Shapiro-Wilk test will be used to assess the normality of the data distribution. Measures of central tendency and dispersion are provided for continuous data as medians (mdn) with associated interquartile ranges (IQR). Summary statistics will be provided for categorical variables and include the number of participants as well as the prevalence within each group.

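### The only between-arm model does not say which term answers Aim 2; name a baseline-adjusted week-10 difference and fix the covariates

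*Combined protocol and SAP*

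**What the plan says.** Aim 2 in section 5 (Study Objectives) is to show that the kiosk is at least equivalent to oral D3 "to raise or maintain serum 25(OH)D levels over a 10-week intervention period". Section 6.5.3 says "Serum 25(OH)D level is the primary endpoint" but gives no time point and does not say whether level or change is meant.

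Section 6.1 plans three 25(OH)D draws: baseline, end of intervention and a later one. The later draw has its own purpose: "25(OH)D is drawn to document sustainment of treatment effect". Section 6.5.1 agrees, calling it "a final level 4 weeks after completing the protocol to evaluate sustainment of the post-treatment level".

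The arms are compared in one sentence of section 6.1, by repeated measures ANOVA "adjusting for significant covariates such as 25(OH)D level at baseline". The logistic regressions in sections 6.1 and 6.4.7 concern relationships among covariates. Section 6.6.1 states "The original analysis plan will be carried out using all available subject data points", restricts the analysis to people with a baseline value and one or more later draws, and adds a normality test and descriptive summaries. It contains no between-arm test, contrast or interval.

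**The concern.** A repeated measures ANOVA with two arms and several visits usually reports a group effect averaged over visits and a group-by-time test. Neither is the week-10 difference. The averaged effect mixes the end of treatment with a draw taken about four weeks after treatment stopped and, if baseline is kept as an outcome, with a visit at which no treatment effect exists. The group-by-time test asks whether the profiles differ; it gives no interval to set against a non-inferiority limit.

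Dilution is harmless to the error rate of a superiority test. In a non-inferiority trial it works in favour of the new device, because a real deficit looks smaller than it is.

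The covariate wording is a lesser matter. Baseline 25(OH)D is named, but only as an example of a covariate that proves significant. The list stays open in a trial where, as section 6.4.6 says, the team knows the assignments.

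**Working it through.** The plan gives no figure to reproduce on this point. It states no SD, margin, alpha or visit correlation, so everything below except the 15-day half-life, the gaps between draws and the required total of 60 is assumed.

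**Step 1: share of the week-10 difference kept by an average of the two follow-up draws.** Suppose both arms decline alike after treatment. The between-arm difference then shrinks by the same factor, and the retained share is a = (1 + 0.5^(gap/half-life))/2.
- Section 6.5.1 states "Serum 25(OH)D has a circulating half-life of 15 days". With a 28-day gap, a = (1 + 0.274)/2 = 0.637. With a 30-day gap (days 70 and 100 in section 6.4.8), a = 0.625.
- At an assumed 30-day half-life, a = 0.75 to 0.76; at an assumed 60 days, a = 0.85 to 0.86.
- With no convergence, a = 1.

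These are scenarios, not limits. Section 6.5.1 also warns that "Serum 25(OH)D levels do not indicate the amount of vitamin D stored in body tissues", so decline could be slower than the half-life implies. Table 1 puts the final kiosk exposure at Time 6, the same visit as the draw, so kiosk levels could move afterwards in a way that supplement levels do not. The share could fall below 0.63 or exceed 1.

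**Step 2: false non-inferiority with a baseline-adjusted average of the two follow-up draws.** Assumed: true week-10 deficit equal to the margin M, M = 3 to 5 ng/mL, SD 7 to 8 ng/mL, equal correlation ρ = 0.5 to 0.8 between visits, 30 per arm (60 split 1:1), one-sided 2.5%.

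The average of two draws has variance SD²(1+ρ)/2, and adjusting for baseline removes SD²ρ². So SE = SD × √((1+ρ)/2 − ρ²) × √(2/30), and the error is P(Z > 1.96 − (1−a)M/SE).

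- Least affected corner (M = 3, SD = 8, ρ = 0.5): SE = 8 × 0.707 × 0.258 = 1.461.
  - a = 0.862: 0.138 × 3/1.461 = 0.283; P(Z > 1.677) = 4.7%.
  - a = 0.637: 0.363 × 3/1.461 = 0.746; P(Z > 1.214) = 11.2%.
- Most affected corner (M = 5, SD = 7, ρ = 0.8): SE = 7 × 0.510 × 0.258 = 0.922.
  - a = 0.862: 0.138 × 5/0.922 = 0.749; P(Z > 1.211) = 11.3%.
  - a = 0.637: 0.363 × 5/0.922 = 1.969; P(Z > −0.009) = 50.4%.
- Week-10 contrast: nothing is averaged in, so the error is 2.5% at every corner.

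**Step 3: if baseline is also averaged in as an outcome.** Assume a margin and true deficit of 0.5 SD and ρ = 0.5 or 0.7. In SD units, SE = √((1+2ρ)/3 × 2/30) = 0.211 or 0.231.
- Deficit fully sustained: the average keeps 2/3 of it, the shift is 0.167/SE, and the error is 12.1% or 10.8%.
- Deficit halves by the last draw: the average keeps 1/2, the shift is 0.25/SE, and the error is 21.9% or 19.0%.

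Here dilution occurs even without convergence.

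**Step 4: covariate selection.** With six unrelated candidates, the chance that at least one reaches p < 0.05 is 1 − 0.95^6 = 26%. The effect on the treatment test is small. In 60,000 simulated trials of 60 people with baseline always included, selection at p < 0.05 gave an error of 2.8% to 2.9%, against 2.5% with baseline only.

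**The case against.** The strongest reply is that nothing in the document proposes an averaged effect. Aim 2 is tied to the 10-week period and the last draw is reserved for sustainment, so a sensible analyst would probably take the week-10 contrast anyway. Section 6.1 also wants the trajectory over three to four months, which a repeated measures model serves. All of this stands. It makes the harm conditional, but it does not supply the missing contrast.

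The percentages rest on assumed inputs and on both arms declining alike. That also stands; they show direction and plausible size only.

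The averaged effect can be more powerful. With no true difference, a margin of 0.5 SD and a sustained effect, simulated power was 59% (ρ = 0.5) or 76% (ρ = 0.7) for the week-10 contrast, against 76% or 88% for the baseline-adjusted average of both draws. That is a real cost, but the average answers a different question from Aim 2.

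Finally, this is a pilot whose first aim is acceptability, and the title page records completion in March 2019. The document nevertheless calls itself a non-inferiority study and sets out to demonstrate Aim 2. If results are already in hand, a contrast named now cannot be described as prespecified and should be reported as chosen afterwards.

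**Conclusion.** The gap in the text is certain: one sentence describes the between-arm analysis, and neither it nor any other section names the term that answers Aim 2. The consequence is conditional. If an average of the two follow-up draws were tested and the arms converged after treatment, false non-inferiority would be about 5% to 11% with 0.86 of the difference retained and about 11% to 50% with 0.637 retained, under the assumptions above.

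A reader might infer more, and the documents do not support it:
- That the planned analysis is biased toward the kiosk. The plan does not commit to an averaged effect.
- That covariate selection materially inflates error. The simulated inflation is negligible; the reason to fix the list is to remove discretion in an unblinded trial.
- That leaving season out of the model biases the comparison. Concurrent block randomisation balances draw date in expectation.

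The point is a cheap improvement that the sponsor should make. It does not make Aim 2 testable by itself: the document states no margin or confidence level, and non-inferiority cannot be concluded without both.

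**What to change.** Replace the ANOVA sentence in section 6.1, and state the same in section 6.6.1, along these lines:
- **Primary analysis:** the between-arm difference in 25(OH)D at week 10, in ng/mL, with its 95% interval, from a likelihood-based repeated measures model of the two follow-up draws with arm by visit and baseline 25(OH)D by visit. This keeps the analysis set and the available-data approach of section 6.6.1.
- **Covariates:** baseline 25(OH)D and any others on a list fixed before the data are analysed, all kept whatever their p-values.
- **Secondary analysis:** the same difference at the later draw, reported for sustainment.
- **Draw definition:** reconcile the timings so that the primary draw is unambiguous. Section 6.1 has 10 and 14 weeks (T6 and T8), Table 1 has T+11wk and T+15wk (Time 6 and Time 7), and section 6.4.8 has days 70 and 100.

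The cost is wording only: no added patients, visits or assays, since everyone analysed must already have a baseline value. The statistical price is the lower power described above when the effect persists. The margin and confidence level should be added as a separate change.

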6.4.7 Prior Concomitant Therapy

Other medications are allowed except those listed in the exclusion criteria (anti-seizure medications, cyclosporine, and idinavir). The research pharmacist will provide expertise for establishing screening criteria to eliminate any potential drug-drug or drug-nutrient interactions. No attempt will be made to control for sun exposure or dietary intake of vitamin D, however, all participants are instructed to refrain from taking any additional supplements containing vitamin D. Volunteers will be asked about vitamin D supplementation during screening and anyone taking a vitamin D supplement in the previous 2 months will not qualify for the study. Both amount of sun exposure and consumption of dietary vitamin D will be captured on surveys. Logistic regression analyses will be used to predict outcomes and explain the interrelationship among the two variables (i.e. sun exposure relationship to 25(OH)D serum levels).

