6.5.2 Appropriateness of Measurements

The Elecsys Vitamin D Total II assay is intended for the quantitative determination of total 25-hydroxyvitamin D in human serum and plasma. The electrochemiluminescence binding assay is intended for use on Elecsys and cobas e immunoassay analyzers.

Body composition measurements, biomarkers, and demographic questionnaires all represent valid and reliable methods to capture data relevant to a vitamin D investigation. All measures have been previously tested and used by this research team.

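### Logistic regression is planned for how covariates relate to serum 25(OH)D, a continuous level, with no category, cut point or blood draw defined for it

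*Combined protocol and SAP*

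**What the plan says.** Section 6.1 (Overall Study Design and Plan) names two analyses. The first is "repeated measures analysis of variance adjusting for significant covariates such as 25(OH)D level at baseline". The next sentence reads "Logistic regression analyses are used to predict outcomes and explain the interrelationships among variables" and spells out what is meant: "age, gender, BMI, body fat, ethnicity, and sun exposure relationship to 25(OH)D serum levels". Section 6.4.7 (Prior Concomitant Therapy) says it again, "Logistic regression analyses will be used to predict outcomes and explain the interrelationship among the two variables", with sun exposure against 25(OH)D as the pair.

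The aim served is Aim 3 in section 5. It names no method and concerns the relation of "gender, age, body mass index, body fat, ethnicity, and sun exposure to serum 25(OH)D levels in both groups". Section 6.5.2 describes the assay as "intended for the quantitative determination of total 25-hydroxyvitamin D in human serum and plasma", and section 6.5.3 makes the serum level the primary endpoint.

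The statistical section, 6.6.1, says "Exploratory data analyses will be conducted on the serum vitamin D levels of participants" and "The Shapiro-Wilk test will be used to assess the normality of the data distribution", and summarises continuous data by medians and interquartile ranges. It mentions neither logistic regression nor any category of 25(OH)D.

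**The concern.** Logistic regression models the odds of falling in a category. Applied to a level in ng/mL, it cannot be fitted until someone decides where to cut the level and which draw to use, and the plan leaves both open.

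This matters in two ways. Splitting the level answers a different question from Aim 3 (who lies above a threshold, not how the level varies with a covariate), and it discards information in a small pilot. Also, a cut and draw chosen after the data are seen give an unrelated covariate several chances to look associated with 25(OH)D. The study is open label (section 6.4.6), so blinding does not protect against such a choice.

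**Working it through.** **Is an outcome category defined anywhere?** Every place where a threshold could be found:

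- 20 ng/mL appears in section 4 as background and in section 6.4.4 as rationale for the supplement dose.
- 30 ng/mL appears in section 4 as the lower end of a background optimum range (30-60 ng/mL), introduced with the remark that sufficiency is debated. It appears in section 6.1 only to explain enrolment at any baseline level.
- Section 6.2 distinguishes sufficient from insufficient participants but gives no number.

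These are two competing values, and neither is attached to an analysis. On timing, sections 6.1 and 6.5.1 give three draws (baseline, 10 weeks, 14 weeks) and assign none to this model. There is no figure of the plan's own to reproduce.

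**Assumptions for size.** The documents give no mean, SD or correlation. Assumed: a normal level, mean 25 or 30 ng/mL, SD 8 or 10 ng/mL, correlation between draws 0.6 or 0.8. Analysed numbers: 60 (section 6.6.2) and 120 × 0.70 = 84.

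**Information kept by a two-way cut** (small effects) = φ(z_p)² / [p(1−p)], where p is the share below the cut.

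- 50/50: 0.3989² / 0.25 = 0.637, a loss of 36%; 60 × 0.637 = 38.
- 80/20: 0.2800² / 0.16 = 0.490, a loss of 51%; 60 × 0.490 = 29.

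| Mean / SD (ng/mL) | Loss, cut at 20 | Loss, cut at 30 |
|---|---|---|
| 25 / 8 | 44.8% | 44.8% |
| 25 / 10 | 41.9% | 41.9% |
| 30 / 8 | 64.7% | 36.3% |
| 30 / 10 | 56.1% | 36.3% |

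**Sparse events.** If the smaller category holds 10% to 50% of 60 people, it contains 6 to 30 events. With one term for each of six covariates that is 6/6 = 1.0 to 30/6 = 5.0 events per term, and fewer if ethnicity has several levels or a group term is added.

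**Chance that one unrelated covariate reaches p<0.05.** Simulation with 20,000 replicates per setting and one normal covariate unrelated to 25(OH)D; logistic likelihood-ratio test against linear t test. Where options are open, the covariate counts as significant if any option gives p<0.05. Only the two follow-up draws were treated as options.

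| Model and what is left open | n = 60 | n = 84 |
|---|---|---|
| Logistic, cut and draw fixed | 5.1-5.7% | 5.0-5.6% |
| Logistic, 20 or 30 ng/mL at 10 weeks | 9.8-10.5% | 9.6-10.4% |
| Logistic, one cut, either follow-up draw | 9.6-10.7% | 8.8-10.3% |
| Logistic, either cut at either follow-up draw | 17.1-19.2% | 16.8-18.6% |
| Linear, draw fixed | 4.8-5.4% | 4.6-5.2% |
| Linear, either follow-up draw | 7.7-9.0% | 7.5-9.0% |

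With the draw fixed, the open cut about doubles the rate. The open draw is a separate gap: alone it still gives 8-9% under a linear model.

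**The case against.** The strongest reply has four parts.

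- **The error rate does not come from logistic regression itself.** With cut and draw fixed it is 5-6%. The increase requires someone to try options and keep the favourable one, and nothing in the document says this will happen. This stands as far as it goes: 17-19% is a ceiling under free choice, and part of it belongs to the open draw. The loss of information does not depend on any such behaviour and remains with cut and draw fixed.
- **Aim 3 is exploratory in a pilot.** No significance threshold is attached to it. This also stands and limits the weight of the point, but a descriptive aim still needs a model that can be fitted and that describes the quantity asked about.
- **A continuous model is already planned.** The covariate clause of the repeated measures analysis gives baseline 25(OH)D only as an example, so others could enter. They could, but the sentence after it assigns the six covariate relations to logistic regression.
- **Sufficiency is a legitimate outcome.** It is in the study title and in the design description. Naming one category, one cut and one draw would cure the lack of specification. It would not recover the lost information, and Aim 3 asks about levels. Sufficiency therefore fits better as an additional, prespecified secondary outcome.

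**Conclusion.** The concern holds. Two sections assign logistic regression to a continuous level, and no section defines the category, cut point or draw that the model requires. Under the assumed means of 25-30 and SDs of 8-10 ng/mL, a cut at 20 ng/mL loses 42-65% of the information and a cut at 30 loses 36-45%. With the draw fixed, leaving the cut open raises the chance of a spurious association for one covariate from 5-6% to 10-11%. The textual mismatch rests on no assumption; the sizes do. The repeated measures comparison of the groups is not affected. The plan should be changed, but the point is confined to a secondary, descriptive aim.

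**What to change.** In sections 6.1 and 6.4.7, replace the logistic regression sentences with wording such as: *Aim 3 will be analysed by linear regression of serum 25(OH)D in ng/mL (log scale if skewed) at the 10-week draw, with group and the listed covariates. Each covariate's slope (for gender and ethnicity, the difference between categories) will be reported with a 95% confidence interval overall and within each group, as descriptive estimates.*

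Three points should be stated with it:

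- Which survey supplies sun exposure. The 10-week update is the one taken at the time of that draw.
- Whether baseline 25(OH)D is in the model. Leaving it out answers Aim 3's question about the level; including it shifts the meaning of the slopes towards change.
- If a sufficiency outcome is also wanted, one cut and one draw, prespecified and labelled secondary.

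A mixed model over all draws is optional. If draw-specific slopes are reported, it needs covariate-by-visit terms, and covariate-by-visit-by-group terms for slopes within groups.

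The cost is wording only, since the 10-week level and all listed covariates are already collected. The drawback is imprecision. For a single covariate, the 95% half-width per 1 SD is t(0.975, n−2) × SD / √(n−1). With SD 8-10 ng/mL this is 2.08-2.61 ng/mL in 60 people and 3.04-3.80 ng/mL in a group of 30, and wider for BMI and body fat, which overlap. Six covariates in two groups give at least 12 slopes. If these were independent, the chance that at least one interval excludes zero with no true effect is 1 − 0.95¹² = 46%, so the intervals should not be read as tests.
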